**7.9.7 Secondary Endpoint #5**

Mitral valve re-intervention at discharge, 6 and 12 months post procedure.

Hypothesis/Decision criteria:

No specific hypotheses or pass/fail criteria have been set. The analysis will be descriptive and no statistical hypothesis test will be performed.

Endpoint Definition/Parameters to Be Estimated:

Mitral valve re-intervention event rate estimate will be provided at discharge, 6 and 12 months post procedure.

Data Collection and Analysis Dataset:

Data will be collected on a RE-INTERVENTION (RE-OP) CRF.

This objective will be analyzed for the Successfully Implanted (IMP) cohort.

Analysis Method:

A Kaplan-Meier analysis will be performed.

The number and percentage of subjects with mitral valve re-intervention post implant on or prior to discharge will also be presented, as described in section 7.2.

**7.9.8 Secondary Endpoint #6**

Stroke at 6 and 12 months post procedure.

Hypothesis/Decision criteria:

No specific hypotheses or pass/fail criteria have been set. The analysis will be descriptive and no statistical hypothesis test will be performed.

Endpoint Definition/Parameters to Be Estimated:

Stroke event rate estimate will be provided at 6 and 12 months post procedure.

Data Collection and Analysis Dataset:

Data will be collected on an AE CRF.

This objective will be analyzed for the Successfully Implanted (IMP) cohort.

Analysis Method:

A Kaplan-Meier analysis will be performed.

**7.9.9 Secondary Endpoint #7**

New onset of atrial fibrillation (AF), as evaluated through follow up ECG at discharge, first follow up (3-6 months) and at second follow up (12 months), as well as on the AE form.

Hypothesis/Decision criteria:

No specific hypotheses or pass/fail criteria have been set. The analysis will be descriptive and no statistical hypothesis test will be performed.

Endpoint Definition/Parameters to Be Estimated:

New onset of AF is defined as when the subject did not present with prior history of AF at baseline nor was AF detected at baseline visit, but AF did manifest post procedure and was either diagnosed during the study visits (discharge, 3-6 months or 12 months visit) or was otherwise diagnosed during the duration of subject participation in the study.

Data Collection and Analysis Dataset:

Data will be collected on a DISCHARGE/FOLLOW UP (SV) CRF or an AE CRF.

This objective will be analyzed for the Successfully Implanted (IMP) cohort.

Analysis Method:

A Kaplan-Meier analysis will be performed.

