## 5.2 Selection of Subjects

### 5.2.1 Study Population

The patient population includes all patients suffering from mitral valve disease, indicated for a mitral valve repair procedure, either as a stand-alone procedure or concomitant to another procedure (for example, coronary artery bypass grafting, tricuspid valve repair, treatment of atrial fibrillation, etc. but excluding patients undergoing aortic valve replacement) and for which the surgeon considers the implantation of a Profile 3D™ or CG Future® Annuloplasty system most appropriate to reconstruct the regurgitant valve.

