#### 7.1.3 Analysis Sets

There are three analysis sets defined for this study. Analysis sets used for each objective are defined in the corresponding objective section. The primary analysis set is the Successfully Implanted analysis set.

- Enrolled analysis set: Composed of all subjects who signed the Patient Informed Consent Form. Time zero begins on the date of informed consent.
- Attempted Implant analysis set (AT): Composed of all enrolled subjects who were attempted for a Profile 3D™ or CG Future® Annuloplasty system implantation. A subject with one or more attempts of the Medtronic study device recorded on the procedure case report form (CRF) is considered as implant attempted. Time zero begins on the date of the first attempted procedure.
- Successfully Implanted analysis set (IMP): Composed of all AT subjects who had either a Profile 3D™ or CG Future® Annuloplasty system implanted successfully. Time zero begins on the date of implant procedure.

All data collected from enrolled, attempted implant, and successfully implanted subjects will be utilized in the analyses as appropriate. Analyses of the primary and secondary endpoints will be descriptive, and no statistical hypothesis tests will be performed.

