### 7.2 General Methodology

Descriptive statistics will be used to report study data. For continuous variables (e.g. age), the mean, median, standard deviation, minimum, maximum, and first and third quartiles will be presented. For categorical variables, the number and percentage of subjects in the category of interest will be presented. For time to event data, Kaplan-Meier analyses of event or event-free rates at discharge, 6 and 12 months will be presented. For these analyses, the time points will correspond to 7 days, 183 days and 365 days post implantation respectively. At each time point with data, the product limit estimate of the event or event-free rates, and the loglog transformed 95% confidence interval using the Peto standard error will be presented. For subjects without an event, the date of censoring will be the latest date of all follow-up visits (including phone and/or mail correspondence), assessments, events (including death) and study exits. For subjects whose exit reason is lost to follow-up, the last follow-up date will be the latest date of the follow-up visits (including phone and/or mail correspondence), assessments and events.

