## 7.4 Handling of Missing, Unused, and Spurious Data and Dropouts

Every effort will be undertaken to minimize missing, unused and spurious data and dropouts. Unless otherwise specified, no statistical techniques will be used to impute missing data. The number of subjects included in each analysis will be reported so that the reader can assess the potential impact of missing data.

In the case of partial dates, if only the month and year are known, the event or assessment will be analyzed as if it occurred on the 15th of that month. If only the year is known, the event or assessment will be analyzed as if it occurred on June 30th of that year. These resolutions of partial dates are subject to the restrictions that events must occur no earlier than the procedure date or after study exit.

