**Data Collection and Analysis Dataset:**

Data will be collected on an ECHOCARDIOGRAM (CV) CRF.

This objective will be analyzed for the Successfully Implanted (IMP) cohort, and for the IMP subjects with CG Future Band, CG Future Ring and Profile 3D Ring respectively. IMP subjects having available MR collection at both baseline and 12 months post procedure will be included in the analysis.

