## **8. Validation Requirements**

Level 1 validation (independent validation) will be used for the analysis datasets and the primary and secondary endpoints. Level 2 validation (peer review) will be used for additional analyses, data summaries, and listings.

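### The new-onset AF Kaplan-Meier is assigned to all implanted subjects, including those with prior or baseline AF who cannot have the event, so the rate is diluted by about the share with AF at entry.

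*Combined protocol and SAP*

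**What the plan says.** - **Event definition (SAP 7.9.9).** New-onset AF requires that the subject "did not present with prior history of AF at baseline nor was AF detected at baseline visit". AF must then appear after the procedure, at a study visit or otherwise during participation.
- **Analysis set (SAP 7.9.9).** "This objective will be analyzed for the Successfully Implanted (IMP) cohort". The method is Kaplan-Meier. The only data sources named are the discharge/follow-up form and the AE form.
- **The implanted set, IMP (SAP 7.1.3).** Attempted subjects in whom a study device was successfully implanted. Baseline rhythm plays no part. The section adds that data from all sets "will be utilized in the analyses as appropriate".
- **Eligibility (SAP 5.2.1 and 5.2.4).** AF is not among the exclusions, and "treatment of atrial fibrillation" is given as an example of an allowed concomitant procedure.
- **Censoring (SAP 7.2).** "For subjects without an event, the date of censoring will be the latest date of all follow-up visits" or other contact. Time-to-event rates are read at days 7, 183 and 365.
- **History of the endpoint.** CIP 13.6 planned a number and percent of subjects, without naming an AF-free denominator. SAP 7.12 records the change to Kaplan-Meier, made to account for censoring, and also names none.

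**The concern.** The definition and the analysis set in 7.9.9 do not fit together. The definition makes only AF-free subjects eligible for the event; the analysis set admits everyone implanted. Once a subject with prior AF is in the analysis, the 7.2 rule treats that subject as event-free and under observation until last contact.

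The resulting curve then depends on two things: the risk of new AF after repair, and how many subjects already had AF at entry. Two registries with the same risk of new AF would report different rates if their AF prevalence at entry differed. A larger sample would not remove the effect. In a study with no hypothesis tests, the estimates are the product, so this bears on what can be said about the endpoint.

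**Working it through.** **Inputs.** N = 200 is the planned sample (SAP section 6), used as an upper bound for the implanted set. The documents give no share b with prior or baseline AF and no at-risk rate r; both are assumed over a range. There is no plan figure to reproduce.

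**Point estimate.** If a share b cannot have the event,

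F_IMP(t) = b × 0 + (1 − b) × F_AF-free(t) = (1 − b) × F_AF-free(t).

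This is exact without censoring, and holds in expectation for Kaplan-Meier when loss to follow-up is equal in the two groups. For example, with b = 30% and r = 20%: 60 subjects have AF at entry, 140 are at risk and 28 have events. Then 28/140 = 20%, but 28/200 = 14%.

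| At-risk rate r | b = 10% | b = 20% | b = 30% | b = 40% |
|---|---|---|---|---|
| 10% | 9% | 8% | 7% | 6% |
| 20% | 18% | 16% | 14% | 12% |
| 30% | 27% | 24% | 21% | 18% |

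**Does censoring change the factor?** In a Kaplan-Meier simulation (N = 1,000,000, half of AF onsets on days 1–7 and half on days 8–365, exit uniform on days 335–395), 0% or 10% loss in both groups gave day-365 ratios of 0.900, 0.800, 0.700 and 0.600 for the four values of b. With 10% loss in AF-free subjects and 40% in prior-AF subjects, the ratio at b = 30% and r = 20% rose from 0.70 to 0.72. The largest excess over 1 − b in any run was 0.027.

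**Intervals.** SAP 7.2 specifies log-log limits with the Peto standard error: Var(S) = S²(1 − S)/n_t, where n_t is the number still at risk at t. On the log(−log S) scale the standard error is √[(1 − S)/n_t] / |ln S|.

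For b = 30%, r = 20%, all followed to day 365:
- IMP: S = 0.86, n_t = 200 × 0.86 = 172. SE = √(0.14/172)/0.1508 = 0.189. Rate 14.0% (9.9–19.6).
- AF-free: S = 0.80, n_t = 140 × 0.80 = 112. SE = √(0.20/112)/0.2231 = 0.189. Rate 20.0% (14.3–27.6).

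At r = 20% with everyone followed to day 365:

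| b | AF-free | IMP as written |
|---|---|---|
| 10% | 20.0% (14.9–26.6) | 18.0% (13.3–24.1) |
| 20% | 20.0% (14.6–27.1) | 16.0% (11.6–21.9) |
| 30% | 20.0% (14.3–27.6) | 14.0% (9.9–19.6) |
| 40% | 20.0% (13.9–28.3) | 12.0% (8.2–17.4) |

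Subjects exit at a 12-month visit with a ±30-day window, so full follow-up to day 365 is optimistic. If half of the event-free subjects have exited by then (n_t = 86 and 56 at b = 30%), IMP gives 14.0% (8.5–22.5) and AF-free gives 20.0% (12.4–31.4).

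The IMP interval therefore excludes the 20% at-risk rate only at b of 30% or more with full follow-up. It includes it at b = 10% and 20%, and at b = 30% when half have exited. At r = 10% no IMP upper limit falls below 10% (b = 40%: 6.0%, 3.5–10.3).

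**The case against.** The best counter-argument is that 7.9.9 is under-specified rather than wrong. Nobody can derive the event without first flagging baseline AF, and "will be utilized in the analyses as appropriate" leaves room to drop those subjects. That wording permits the restriction but does not state it, and the set that 7.9.9 does name is all of IMP. Section 8 says "Level 1 validation (independent validation) will be used for the analysis datasets and the primary and secondary endpoints"; double programming may expose two readings but does not say which was intended.

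It can also be said that new AF per implanted subject is a legitimate descriptive quantity, close to the percentage in the CIP. That is fair, but the CIP endpoint text calls it an incidence, and nothing in the SAP would label it as a rate that includes subjects not at risk. SAP 7.9.3 tabulates cardiac rhythm and risk factors for the same cohort, so a reader could rescale roughly, but only if AF history is shown, and rescaling does not give the AF-free interval.

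Several smaller points stand:
- SAP 7.2 sets censoring dates; it does not itself decide who enters the risk set. The problem comes from the set named in 7.9.9.
- The restrictions within IMP written out elsewhere, such as "IMP subjects having available MR collection at both baseline and 12 months post procedure will be included in the analysis" in 7.9.1, concern data availability, not being at risk. They show that the SAP states subsets in endpoint sections, and no more.
- The two intervals estimate different quantities, so one excluding the other's rate is not a coverage failure.
- The CIP baseline lists (9.1 and 9.9.1) name cardiac rhythm and clinical history but not AF history as an item.

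**Conclusion.** The concern holds. As written, the endpoint #7 rate is about (1 − b) times the rate among subjects who could develop new AF. The form of the dilution is firm; its size is not, because b and the AF rate are assumed throughout. The exact factor also rests on similar loss to follow-up in the two groups; heavier loss among prior-AF subjects raised the ratio by at most 0.027 in the cases run.

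This should be corrected, but it is not critical. The endpoint is secondary and descriptive, and no test, pass/fail criterion or sample size depends on it.

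**What to change.** In SAP 7.9.9, state that endpoint #7 is analysed in implanted subjects with no history of AF and no AF at the baseline visit, and name the baseline forms that supply this. SAP 7.4 already requires the number analysed to be reported.

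Because 7.4 says "no statistical techniques will be used to impute missing data", also state what happens when baseline rhythm or AF history is missing. One option is to leave these subjects out of the main analysis, give their number, and include them in a sensitivity run; the sensitivity run is optional.

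The cost is one or two sentences and a derived flag. Baseline rhythm and clinical history are already collected; the team should confirm that the history form records AF, which the event definition needs in any case. The interval widens because the risk set is smaller. At b = 30% it is 140 of 200. For the same 20% rate with full follow-up, the interval is 14.3–27.6% at n = 140 and 15.1–26.2% at n = 200, and 13.3/11.1 = 1.20. The corresponding factors are 1.12 at b = 20% and 1.30 at b = 40%. That width reflects the number of subjects truly at risk.

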**7.9.10 Secondary Endpoint #8**

Number of attempts required for procedural success, and bypass time as a measure of procedural complexity, as measured by standard operating room procedures at the site.

Hypothesis/Decision criteria:

No specific hypotheses or pass/fail criteria have been set. The analysis will be descriptive and no statistical hypothesis test will be performed.

Endpoint Definition/Parameters to Be Estimated:

Number of attempts required for procedural success, and bypass time as a measure of procedural complexity.

Data Collection and Analysis Dataset:

Data will be collected on an IMPLANT (IMP) CRF.

This objective will be analyzed for the Successfully Implant (IMP) cohort.

**Analysis Method:**

The number of attempts (per subject) required for procedural success and the bypass time will be summarized. Descriptive statistics will be provided.

## **7.10 Safety Evaluation**

Primary and secondary safety endpoints will be summarized as noted in Section 7.9 of this Statistical Analysis Plan (SAP). Adverse events will be provided in a listing for all attempted implant subjects. The proportion of subjects experiencing events will also be summarized by MEDDRA coding (System Organ Class and High Level Term) for successfully implanted and attempted but not successfully implanted subjects.

## **7.11 Health Outcomes Analyses**

No health outcomes analyses are planned.

## **7.12 Changes to Planned Analysis**

Analysis set defined in the CIP for the primary and secondary endpoints is changed to the Successfully Implanted set in order to align with other surgical valve studies.

New onset of atrial fibrillation will be evaluated using Kaplan-Meier method instead of percent of subjects as described in the CIP in order to incorporate subject censoring in the course of the study. Atrial fibrillation identified on the post-procedural ECG or AE forms will be included in the analysis.

Changes to V1.0 of the SAP include: Baseline data will be presented for the Enrolled and Successfully Implanted cohorts, and procedural data will be presented for the Attempted Implant and Successfully Implanted cohorts. As one of the objectives of the registry is to characterize subjects who are considered eligible for mitral valve repair in South Asia, analyzing baseline and procedural characteristics on these analysis cohorts will cover the populations of interest.

Sub-group analyses will be performed on the Successfully Implanted subjects with CG Future Band, CG Future Ring and Profile 3D Ring respectively for the primary and selected secondary endpoints.

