## 5.2. Endpoints

### 5.2.1. Primary Endpoint

To evaluate clinical outcomes at 12 months post procedure:

1. Improvement in MR (grade)

This will be determined by assessing the level of mitral valve regurgitation using echo, in subjects at 12 months post procedure compared to the level at baseline. The levels of regurgitation, level 0-4, will correspond to the ASE guidelines ranging from no MR, Mild MR, Moderate MR, Moderate-to-Severe MR and Severe MR, as described in Table 1 above.

2. All cause mortality

All deaths occurring from any cause post procedure.

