## **13. Statistical Design and Methods**

The statistical analyses will be performed by Medtronic employed statisticians. Three study populations are defined:

- Enrolled: Composed of all patients who signed the Patient Informed Consent Form.
- Attempted Implant (AT): Composed of all enrolled subjects who are attempted for a Profile 3D™ or CG Future® Annuloplasty system implantation. Time zero begins at the date of attempted procedure.
- Implanted (IMP): Composed of all AT subjects who had either a Profile 3D™ or CG Future® Annuloplasty system implanted. Time zero for implanted subjects begins at the date of implant procedure.

All data collected from enrolled, attempted implant, and implanted subjects will be utilized in the analyses as appropriate. Analyses of the primary and secondary endpoints will be descriptive, and no statistical hypothesis tests will be performed.

All continuous variables will be summarized as the number of subjects, means, standard deviations, medians, minimums, maximums, and interquartile ranges. Categorical variables will be summarized as frequencies and percentages.

Additional details of planned statistical analysis will be specified in Statistical Analysis Plan (SAP). Any deviations from the original statistical plan will be summarized in the Clinical Study Report(s) (CSRs), along with the justification for the deviations.

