## 6. Determination of Sample Size

The sample size of 200 subjects who are eligible and intended to be implanted with a Profile 3D™ or CG Future® Annuloplasty system in the surgical repair procedure is adequate and appropriate for the evaluation of local evidence and obtaining real world data on clinical outcomes following implantation of these two products. This sample size was not statistically derived as this is not a hypothesis driven study.

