## 7.7 Treatment Characteristics

Procedural data will be summarized for the Attempted Implant and Successfully Implanted analysis sets. Continuous variables will be summarized with means, medians, standard deviations, minimums, maximums, and first and third quartiles. Categorical variables will be summarized with frequencies and percentages.

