**Data Collection and Analysis Dataset:**

Data will be collected on an AE CRF.

This objective will be analyzed for the Successfully Implanted (IMP) cohort, and for the IMP subjects with CG Future Band, CG Future Ring and Profile 3D Ring respectively.

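### SAP 7.9.2 estimates 12-month all-cause mortality only in successfully implanted subjects; a supportive attempted-implant result should stand beside it

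*Combined protocol and SAP*

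**What the plan says.** CIP 5.2.1 describes the mortality endpoint as "All deaths occurring from any cause post procedure". CIP section 13 defines three populations (enrolled, attempted implant, implanted), to be used as appropriate, and assigns none of them to mortality.

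SAP 7.1.3 makes the Successfully Implanted set (IMP) the primary analysis set: "Composed of all AT subjects who had either a Profile 3D™ or CG Future® Annuloplasty system implanted successfully". It also defines the Attempted Implant set (AT), which needs only one recorded attempt with a study device, and gives it its own origin: "Time zero begins on the date of the first attempted procedure".

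For mortality, SAP 7.9.2 says: "This objective will be analyzed for the Successfully Implanted (IMP) cohort, and for the IMP subjects with CG Future Band", followed by the two ring subgroups. The method is Kaplan-Meier. No AT estimate is named.

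SAP 7.12 announces the choice, "Analysis set defined in the CIP for the primary and secondary endpoints is changed to the Successfully Implanted set", and gives alignment with other surgical valve studies as the reason.

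Other sections do look beyond IMP. SAP 7.7: "Procedural data will be summarized for the Attempted Implant and Successfully Implanted analysis sets". SAP 7.1.1 counts subjects attempted, implanted and died. SAP 7.10 lists adverse events for all AT subjects and tabulates event proportions separately for those attempted but not successfully implanted.

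**The concern.** Membership of IMP is decided by how the operation ended. A patient in whom a study device was tried, not finally implanted, and who then died is removed from a primary safety endpoint because of that result. The planned figure answers one question: how many patients die within a year once a device is in place? It does not answer another: how many die within a year of an attempted repair with one of these devices? The second question also fits CIP 5.2.1, which does not make the endpoint conditional on implant success.

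A reader of the registry report would want to know whether the two answers differ. The plan offers counts, listings and proportions by MedDRA term, from which a crude tally might be assembled. It gives no 12-month AT rate and no interval.

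**Working it through.** **Plan's own figure.** There is none to reproduce. The 200 subjects were not statistically derived (CIP 13.4, SAP 6), and no expected mortality or failed-attempt rate is stated.

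**Where a death is counted**

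| Death | Primary endpoint #2 | Elsewhere |
|---|---|---|
| In an IMP subject | Yes, SAP 7.9.2 | Disposition; AE listing; MedDRA proportions |
| In an AT subject not in IMP | No, neither numerator nor denominator | The same three outputs, with no 12-month rate or interval |

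**Size of the difference.** Let f be the share of attempts that finally fail, mF the 12-month mortality after such a failure, and mI the 12-month mortality in IMP. Then

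AT mortality = (1 - f) × mI + f × mF, so AT - IMP = f × (mF - mI).

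All three inputs are assumptions: mF 0 to 30%, mI 3 to 5%. For orientation only, CIP 4.1 cites a 30-day mortality of 3.3% in one series with cardiomyopathy; that is not a 12-month rate for this registry.

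| f | Lowest (mF 0%, mI 5%) | Highest (mF 30%, mI 3%) |
|---|---|---|
| 2% | 0.02 × (0 - 5) = -0.1 points | 0.02 × (30 - 3) = +0.5 points |
| 10% | 0.10 × (0 - 5) = -0.5 points | 0.10 × (30 - 3) = +2.7 points |

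The difference is zero when mF equals mI, and its sign follows mF - mI.

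**Worked example, no censoring.** Assume 200 attempts, 10 final failures with 2 deaths, and 6 deaths among the 190 implanted.

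- IMP: 6/190 = 3.2%. Exact 95% interval 1.2 to 6.7; SAP 7.2 method (log-log with Peto standard error, S × √((1 - S)/number at risk), 184 at risk) 1.4 to 6.9.
- AT: 8/200 = 4.0%. Exact 1.7 to 7.7; SAP method (192 at risk) 2.0 to 7.8.
- Check: f = 10/200 = 5%, mF = 2/10 = 20%, so 0.05 × (20 - 3.2) = 0.8 points, which matches 4.0 - 3.2.

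The intervals overlap widely.

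**Early exit.** Take the same example, with surviving failed-attempt subjects leaving at day 7. Of the 6 IMP deaths, 3 occur by day 7 and 3 later. After day 7, 187 IMP subjects remain at risk, so the later factor is 184/187.

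| Failed-attempt deaths seen before exit | AT survival | AT mortality |
|---|---|---|
| 2 | 195/200 × 184/187 | 4.1% |
| 1 | 196/200 × 184/187 | 3.6% |
| 0 | 197/200 × 184/187 | 3.1% |

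If neither death is seen, the AT curve falls just below the IMP figure of 3.2%, although the true AT proportion in the example is 4.0%. The curve alone can therefore mislead, and the crude count and censoring times need to come first.

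**The case against.** The case for leaving the plan alone is substantial.

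- *IMP fits the objective.* The registry studies outcomes of two products, and SAP 6 speaks of "obtaining real world data on clinical outcomes following implantation of these two products". A late death in a patient who left theatre without a study device says little about those products. This stands, and it is why IMP should remain primary. The same sentence in SAP 6 also describes the sample as subjects intended to be implanted, so it does not rule out an AT view.
- *No rule is broken.* A reader might infer that the SAP departs from a protocol-mandated set. The documents do not support that. CIP 13 assigns no set to mortality, CIP 5.2.1 says which deaths count without naming a denominator, and SAP 7.12 discloses the choice. CIP 9.11, which keeps subjects who discontinue after an attempted implant in the analysis, does so only as appropriate and also covers implanted subjects, so it adds little.
- *The deaths are visible.* A reader might infer that they go unreported. They do not: SAP 7.1.1 and 7.10 cover them. What is missing is a rate with an interval.
- *The numbers are assumed.* This stands. Several attempts in one subject are foreseen (secondary endpoint #8), and a subject whose later attempt succeeds is in IMP. Only final failures matter, and the documents give no basis for a share as high as 10%.
- *A Kaplan-Meier curve may be the wrong tool.* This stands in part. For a handful of subjects with uncertain follow-up, the count is the more reliable item.

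**Conclusion.** The point holds as a modest, inexpensive improvement. Primary endpoint #2 is conditional on implant success, and no attempted-implant mortality rate or interval is planned. Because the analysis is descriptive and has no pass/fail criterion, no decision turns on it; what is affected is how completely a primary safety endpoint is described.

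Its size cannot be fixed from the documents. Under the assumed mortalities above, AT minus IMP is about -0.1 to +0.5 points at 2% final failures and -0.5 to +2.7 points at 10%. The upper figure needs both a 10% failure share and 30% mortality after failure.

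Two stronger readings should be avoided. First, one might conclude that the plan understates mortality. That is true only if mortality after a failed attempt exceeds mortality in IMP, and the documents give neither figure. Second, one might treat the added word in SAP 7.1.3 as an error, since the CIP has "Composed of all AT subjects who had either a Profile 3D™ or CG Future® Annuloplasty system implanted" while the SAP requires the implant to be successful and states no criterion. That is a missing detail, not a defect in its own right. AT membership depends only on a recorded attempt, so an AT result would not be affected by how the word is read.

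**What to change.** Keep IMP, with its device subgroups, as the primary analysis in SAP 7.9.2. Add a supportive AT mortality result, with time zero at the first attempted procedure (already the AT origin in SAP 7.1.3) in place of the post-implantation clock in SAP 7.2. Report in this order:

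1. The number of AT subjects not in IMP, their crude number of deaths, and their censoring times.
2. The AT Kaplan-Meier estimate at 12 months, with the interval method of SAP 7.2.
3. A note that the AT estimate is informative mainly for early deaths. CIP 9.11 encourages all subjects to stay to 12 months and takes explanted subjects out of the study, but no section states that subjects left without a study device are followed for 12 months.

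The cost is a few lines of SAP text and one more table. The AT set and its time zero already exist, no new data are requested, and the alignment with other surgical valve studies cited in SAP 7.12 is kept. The downside is that the AT figure may be slightly less favourable than the IMP figure.
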